Scientific background: When exercise training is adequately supervised and adherence is high, it has a therapeutic effect in individuals with prediabetes or type 2 diabetes mellitus (T2DM) (Little et al., 2011; Johansen et al., 2017). Many of the cardiometabolic risk factors associated with T2DM can be improved or ameliorated with weight control and diet, as well as with regular exercise. Indeed, the beneficial effects of high-intensity interval (HIIT) and resistance (RT) training on insulin resistance have been extensively studied at the level of skeletal muscle and adipose tissue (Zanuso et al., 2017). Notwithstanding the irrefutable clinical benefits of exercise in general, there is known to be individual variability in the response to different exercise interventions (Bouchard et al., 2012b), including CT (Stephens et al., 2015). Whereas some individuals, the so-called ‘responders’ improve their metabolic profile after a training intervention (*e.g.*, a decrease in fasting glucose) others, the ‘non-responders’ show no response or even an opposite response (Boulé et al., 2005). From a statistical viewpoint, a non-response for a given variable is a lack of difference between a control and a treatment condition. The non-responder phenomenon has been shown in a non-negligible proportion of participants in exercise intervention studies, for instance, in 4–9% of adults at risk for T2DM (Phillips et al., 2017) or in 21% of patients with T2DM (Stephens et al., 2015). **Objectives:** To investigate the effects of a 20-week CT intervention on cardiovascular risk factors such as body composition, blood pressure and lipid profile among adult women with hyperglycaemia. A secondary aim was to report prevalence of non-responders for the different study outcomes. **Design:** An experimental, and randomized control clinical study. **Methods:** Physically inactive overweight/obese and hyperglycaemic adult women between 20 and 50 years, will be randomly assigned to a 20-weeks of an exercise intervention group or to a control (non-exercise) group. Comorbidities indices for body composition [body mass, waist circumference (WC), fat and lean mass], blood pressure and metabolic profile (total, LDL- and HDL-cholesterol, triglycerides, and fasting glucose) will be assessed before and after the 20-week intervention. The clinical trials will be taken in the Family Healthcare Center *Tomás Rojas* of the city of Los Lagos, Chile, which is a public healthcare centre of this country. We hope to apply the following eligibility criteria a) age between 30 and 59 years, b) not living in a rural area, c) physical activity levels [as assessed by the International Physical Activity Questionnaire (IPAQ) < 600 metabolic equivalents (MET)·min/week, d) non-involvement in regular exercise during the previous 6 months, e) fasting glucose of 100–125 mg/dL, and f) 1+ values above (or below for HDL-cholesterol) normal cutoffs for: body composition [*i.e.*, WC >

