
Statistical Analysis Plan (SAP): We will apply 2 main forms of statistical analyses a) to report the pre-post changes in mean terms, and b) to report the results according with the inter-individual responses based on the technical error criteria, where according with the error calculated in the three previous measurements registered by the sample that was voluntary. Thus, for example, we will classify the subjects in responders and non-responders by the technical error of measurement, and additionally, we will classify the subjects according with a responder and non-responder clinical criteria, where we will classify as responders to all subjects who can be able of changing an initial adverse clinical altered profile for a healthy new classification. Thus, the specific statistical methods that we hope to apply for each analysis are; test of normality and homoscedasticity assumptions using Shapiro-Wilk and Levene's tests, the Student's *t* test for the identification of differences at baseline. An ANCOVA will be conducted (for potential confounders outcomes) in those altered baseline differences outcomes. We also hope to apply the repeated measures of two-way (group, time) to assess occurrence of an actual training effect [*i.e.*, $p < 0.05$ for the interaction (group \times time) for the different study outcomes]. Among the specific statistical methods we hope to apply the Bonferroni *post hoc* test we hope to apply when we can be seen test differences among groups. Similarly, we hope to apply the Cohen's *d* test in order to detect effect size, using the threshold values of 0.20, 0.60, 1.2, and 2.0 for small, moderate, large, and very large effects, respectively (Hopkins et al., 2009), with 95% confidence intervals (CI). The alpha level was fixed at $P < 0.05$ for statistical significance.

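### The additional clinical responder classification defines neither the non-responder nor the denominator; read literally and per marker, it counts women already healthy on a marker as non-responders on it

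*Combined protocol and SAP*

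**What the plan says.** The Objectives in the protocol set the secondary aim: "A secondary aim was to report prevalence of non-responders for the different study outcomes". They do not say which definition of non-response it uses.

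The Statistical Analysis Plan then gives two classifications. The first is "we will classify the subjects in responders and non-responders by the technical error of measurement". The second is introduced as additional: "we will classify the subjects according with a responder and non-responder clinical criteria". For this second one, the rule is "we will classify as responders to all subjects who can be able of changing an initial adverse clinical altered profile"; that is, a responder is a woman "changing an initial adverse clinical altered profile for a healthy new classification". The SAP does not define the clinical non-responder, state a denominator, or say what happens to women who are healthy at baseline.

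Two eligibility criteria in the Methods matter here. All women must have "e) fasting glucose of 100–125 mg/dL". Beyond that they need only "1+ values above (or below for HDL-cholesterol) normal cutoffs for" waist circumference, blood pressure or blood lipids. The background section also describes non-response, statistically, as no difference between a control and a treatment condition.

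**The concern.** The clinical split has two classes and is applied to the subjects as a group. Only one class is defined, so the natural way to fill the other is with everyone else. A woman who enters on waist alone may be normal on systolic and diastolic pressure, total, LDL and HDL cholesterol, and triglycerides. She cannot make the move that defines a responder on any of those six, whatever the training does.

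If she stays in the denominator, the clinical non-responder prevalence partly measures how many women started healthy. Two markers on which the same share of adverse women normalise would show different prevalences purely because of their baseline mix. Such figures would also be hard to set beside the 4–9% and 21% that the background cites from other studies. If the denominator stays unstated, it can be chosen after the data are seen.

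A second, separate weakness is that no control comparison is stated for the clinical rule. A woman who crosses a cutoff through ordinary day-to-day variation counts as a responder.

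**Working it through.** The documents give no expected responder rate, no baseline share adverse per marker and no sample size, so there is no planned figure to reproduce. The inputs below are assumptions unless marked as coming from the documents.

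**1. Denominator**

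- p = share of women adverse on a marker at baseline. From the documents, p = 100% for fasting glucose, by eligibility. For waist, blood pressure and lipids it is unknown.
- c = share of adverse women who become healthy on that marker. Unknown.

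Non-responder prevalence over all women = 1 − p × c. Among women who could respond it is 1 − c. Inflation = (1 − p × c) − (1 − c) = c × (1 − p).

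With an assumed c = 30%, prevalence among women who could respond is 1 − 0.30 = 70%. Over all women:

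| p | 1 − p × c | Inflation (points) |
|---|---|---|
| 20% | 1 − 0.06 = 94% | 24 |
| 40% | 1 − 0.12 = 88% | 18 |
| 60% | 1 − 0.18 = 82% | 12 |
| 80% | 1 − 0.24 = 76% | 6 |
| 100% | 1 − 0.30 = 70% | 0 |

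Over p from 20% to 80% and c from 20% to 80%, inflation runs from 0.20 × 0.20 = 4 points to 0.80 × 0.80 = 64 points.

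**2. Where this applies**

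- Waist, blood pressure and lipids: yes, because a woman may be healthy on any one of them at entry.
- Fasting glucose: no, because p = 100% at entry.
- Body mass, fat mass and lean mass: the clinical rule cannot be applied, since the documents give no cutoff.
- Technical-error classification: no, since it does not depend on the baseline category.

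**3. Chance crossing, glucose as the example**

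Assume true values are normal between women, and that the screening and retest readings each add independent normal error. Women are selected on one screening reading of 100–125 mg/dL and true values do not change. The quantity is P(retest < 100 | screening 100–125).

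| Assumed mean (mg/dL) | Between-woman SD | Within-woman SD | Below 100 on retest |
|---|---|---|---|
| 100 | 10 | 7 | 27.6% (highest) |
| 104 | 12 | 5 | 14.7% (lowest) |

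These are the extremes over means of 100–104, between-woman SD 10–12 and within-woman SD 5–7, so about 15–28%. With the same SDs and an assumed mean of 110, the range is about 9–14%. These women would be called responders with no true change, so this effect lowers non-responder prevalence. It acts in the opposite direction to the denominator effect.

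**The case against.** The strongest reply is that the SAP never says women healthy at baseline are non-responders. Its responder definition starts from an adverse state, so it could equally be meant only for women in that state, and then nothing is inflated. This stands: the fault is an undefined non-responder and denominator, and the inflation follows from only one reading. But limiting the denominator is something the reader has to add.

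The word profile could also mean the overall profile. Every woman is then adverse at entry and the denominator problem disappears. However, a prevalence for each outcome, as the secondary aim asks, needs a classification for each outcome.

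A reader might infer that the secondary aim itself will yield a wrong number. The documents do not support that. The aim names no rule, and the SAP gives technical error first and the clinical rule as an addition.

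A reader might also infer that most women start healthy on most markers. Criterion (f) sets a minimum, not a distribution. In an overweight or obese population with a waist cutoff of 80 cm, the adverse share for waist may be high and the inflation there small.

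Finally, it is fair to say that a between-arm difference answers a different question from a descriptive prevalence. It should therefore stand beside the prevalence, not replace it. It does fit the protocol's own description of non-response.

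**Conclusion.** The point holds as a gap in definition with a real consequence under the literal, per-marker reading. For waist, blood pressure and lipids, that reading inflates clinical non-responder prevalence by c × (1 − p). At an assumed c of 30%, this is 6 to 24 points for p from 80% down to 20%. The actual size cannot be found from the documents, because neither p nor c is given. It is zero if women healthy at baseline are left out of the denominator.

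The missing control comparison is a separate weakness that works the other way. Its illustration, about 15–28% or about 9–14% depending on the assumed mean, rests entirely on assumed means and SDs. The two effects should not be added together or described as one bias.

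The matter is worth correcting because it concerns reported results and is cheap to settle before analysis. It does not touch the analysis of mean changes.

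**What to change.** Add to the SAP that, for each marker with a stated cutoff, clinical responder and non-responder proportions are calculated only among women adverse on that marker at baseline. Apply this identically in both arms and show the number at risk in each. Beside the descriptive prevalence, give the exercise-minus-control difference in the responder proportion with a 95% CI, so that chance crossing, expected in both arms, is set against the control group. State which classification serves the secondary aim, and that the clinical one is not applied to body mass, fat mass and lean mass unless cutoffs are specified.

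A separate table for women healthy at baseline, showing who stayed healthy and who became adverse, is optional.

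The cost is a few sentences and a revised table, with no new measurements, since these outcomes are already assessed before and after the intervention. The price is smaller denominators and wider intervals per marker, most of all for markers on which few women start adverse.

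### ANCOVA is kept for outcomes that differ at baseline, its covariate is unclear, and no rule says which result counts when such an outcome also has an interaction test

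*Combined protocol and SAP*

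**What the plan says.** The Methods randomise women to "an exercise intervention group or to a control (non-exercise) group". Outcomes "will be assessed before and after the 20-week intervention", so each has two time points.

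The Statistical Analysis Plan then lists three steps that bear on this point:

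- Student's t "test for the identification of differences at baseline".
- "An ANCOVA will be conducted (for potential confounders outcomes) in those altered baseline differences outcomes". That the t test is what flags an outcome for ANCOVA is inferred from the order of the sentences; the SAP does not say so outright. The parenthesis is the only description of the covariate. It could mean the outcome's own baseline value, other outcomes that differ at baseline, or other confounders.
- "We also hope to apply the repeated measures of two-way (group, time) to assess occurrence of an actual training effect". A group-by-time interaction with p below 0.05 is the stated sign of such an effect, and it applies to the study outcomes generally.

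Nothing says whether ANCOVA replaces the interaction test for a flagged outcome or is added to it.

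**The concern.** Whether an outcome is adjusted for baseline appears to depend on a significance test of baseline balance. In a randomised comparison that test is positive by chance about 5% of the time, and it says little about how useful adjustment would be. The value of adjustment depends on how well baseline predicts the 20-week value, and that is just as relevant for outcomes the t test passes over.

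Two things are at stake. First, unflagged outcomes receive only a change-score test, which can waste precision. Second, a flagged outcome may end up with two results, and these are most likely to disagree when baseline differs. With no order of precedence, the choice could be made after both are seen.

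**Working it through.** **Inputs.** From the documents: two groups, two time points, significance at 0.05 ("The alpha level was fixed at $P < 0.05$ for statistical significance"), and 11 outcomes: four for body composition ("body mass, waist circumference (WC), fat and lean mass"), systolic and diastolic pressure, and five metabolic. The documents give no sample size, SD, effect size or pre-post correlation, so there is no planned figure to reproduce. Assumed: 20 per arm, 1:1 allocation, two-sided testing, normal data, effect 0.6 baseline SD, correlation rho from 0.5 to 0.9, and ratio s = SDpost/SDpre of 1.0 or 1.2.

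**Step 1: the interaction is a change-score test.** With two groups and two times, the interaction F equals the squared t for change. Two simulated data sets gave 4.996 = 4.996 and 3.951 = 3.951.

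**Step 2: what governs the gain.** Set baseline SD to 1 and let beta = rho × s.

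- Residual variance of the 20-week value given baseline: R = s²(1 − rho²).
- Variance of the change: s² + 1 − 2·rho·s = R + (1 − beta)².
- ANCOVA/change variance ratio: [R / (R + (1 − beta)²)] × [1 + 1/(2n − 4)].

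The second factor is the price of estimating the slope: 1 + 1/36 = 1.028 at 20 per arm and 1 + 1/16 = 1.0625 at 10. ANCOVA gains only if (1 − beta)²/R exceeds 1/(2n − 4), which is 0.028 at 20 per arm.

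| s | rho | beta | (1 − beta)² | R | variance ratio | power, change → ANCOVA |
|---|---|---|---|---|---|---|
| 1.0 | 0.5 | 0.50 | 0.2500 | 0.7500 | 0.771 | 46% → 56% |
| 1.0 | 0.7 | 0.70 | 0.0900 | 0.5100 | 0.874 | 67% → 72% |
| 1.0 | 0.8 | 0.80 | 0.0400 | 0.3600 | 0.925 | 83% → 86% |
| 1.0 | 0.9 | 0.90 | 0.0100 | 0.1900 | 0.976 | 99% → 99% |
| 1.2 | 0.5 | 0.60 | 0.1600 | 1.0800 | 0.895 | 39% → 42% |
| 1.2 | 0.7 | 0.84 | 0.0256 | 0.7344 | 0.993 | 56% → 57% |
| 1.2 | 0.8 | 0.96 | 0.0016 | 0.5184 | 1.025 | 73% → 72% |
| 1.2 | 0.9 | 1.08 | 0.0064 | 0.2736 | 1.004 | 94% → 93% |

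Power is simulated, 40,000 trials per setting. Power of the rule that uses ANCOVA only for flagged outcomes is within 0.3 points of the change score in these rows, so the gate itself matters little. The gain comes from adjusting everything.

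**Step 3: fasting glucose.** The entry window ("fasting glucose of 100–125 mg/dL") narrows the baseline SD but not the residual spread. Assume unselected means of 95 to 115, SDs of 10 to 20 and rho of 0.5 to 0.9. After selection the baseline SD is 5.0 to 7.0, and the ANCOVA/change variance ratio runs from 0.903 to 1.022: a 10% saving to a 2% loss. Beta alone does not settle it. With beta 0.5, unselected SD 20 and selected baseline SD 7, (1 − beta)² × 7² = 12.25 and R = 0.75 × 400 = 300. The ratio is then 1.028 × 300/312.25 = 0.99, a saving of about 1%.

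**Step 4: overall error rate.** With no true effect, the gated rule rejects in about 4–5% of trials.

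**Step 5: flagged outcomes.** If the groups are as randomised, 5% of comparisons are flagged. With 11 outcomes that is 11 × 0.05 = 0.55 expected, and the chance of at least one is 1 − 0.95¹¹ = 43% if they were independent, which related lipid and body-size measures are not.

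Given the standardised baseline difference z, the null change-score statistic has mean (beta − 1)z/√v and variance R/v, with v = R + (1 − beta)². At s = 1.0 and rho 0.5, v = 1. The average |z| beyond 1.96 is about 2.34, so the mean is −1.17 and the SD 0.866. The chance of passing −1.96 is Φ(−0.79/0.866) = Φ(−0.91), about 18%. Averaging over all |z| above 1.96 gives 18.5%, 13.0% and 7.6% at rho 0.5, 0.7 and 0.9. Simulation at 20 per arm gives 18–19%, 12–13% and 7–8%, against about 5% for ANCOVA.

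With the 0.6 SD effect and s = 1.0, the two verdicts differ in about 40%, 29% and 2.5% of flagged comparisons at rho 0.5, 0.7 and 0.9. As a share of all comparisons that is 0.05 × 0.40 = 2% down to 0.05 × 0.025 = 0.1%.

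**The case against.** The strongest reply is that the SAP already names its criterion. A significant interaction marks a training effect for the study outcomes, with no exception for flagged ones, and the sentence is introduced as a further step, which suggests that ANCOVA supplements it. That stands. A reader might infer that no deciding analysis is named at all, and the text does not support this. The gap is limited to precedence for flagged outcomes.

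The planned test is also valid and unbiased over randomisation. A reader might take the raised rejection rates in flagged outcomes for an inflated trial-wide error rate. They are not: they apply to about 5% of comparisons and are offset elsewhere.

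The size of the gain is uncertain. Much larger gains can be computed with a 20-week SD smaller than the baseline SD, but nothing in the documents supports a ratio below 1, and the glucose window points the other way (1.13 to 2.58 under the assumptions above). It is also tempting to say that adjustment pays whenever beta is well below 1; the glucose example shows otherwise.

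The covariate wording can be read as adjusting for the outcomes found to differ at baseline, so the covariate is unclear rather than wholly absent.

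What remains is an apparent baseline-test gate, an unclear covariate, no precedence rule, and precision that may be given up for no benefit.

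**Conclusion.** The point holds as an improvement worth making; it does not invalidate the plan. Three textual findings need no assumptions: ANCOVA is limited to outcomes with a baseline difference, its covariate is not clearly identified, and no rule settles which result counts where a flagged outcome has both analyses. That the t test is the trigger is an inference.

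The size rests on assumed values throughout. At a post/pre SD ratio of 1.0, adjusting every outcome is worth about 10 power points at rho 0.5, 5 to 6 at 0.7, and almost nothing at 0.9. At ratio 1.2 it is worth 3 to 4 points at rho 0.5 and is nil or slightly negative from 0.7–0.8 up. The frequency of flags assumes groups as randomised. The protocol analyses only exercisers with at least 70% compliance, so the analysed groups may differ at baseline for reasons other than chance, and the true frequency is unknown.

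**What to change.** - Drop the baseline t tests as a trigger and present baseline data descriptively.
- For every outcome, estimate the effect by ANCOVA of the 20-week value on group, with that outcome's own baseline value as covariate.
- Report the adjusted difference with its 95% confidence interval.
- Name this as the single deciding analysis, in place of the interaction test.

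The cost is SAP wording only. Baseline values are already collected, and no extra participants are needed. The statistical downside is at most about 3% more variance at 20 per arm (about 6% at 10 per arm), where (1 − beta)² is small relative to the residual variance. The change does not cure the compliance exclusion, which needs its own remedy.
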